1.1 Objective

The purpose of this pilot study is to assess the feasibility and acceptability of acupressure in patients with rheumatoid arthritis (RA). This study will allow us to better estimate the needed sample size and to focus on specific primary outcome measures for future studies.

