1.4.2 Assessments. Pre-screening and recruitment will occur virtually or in-person in clinic. Trained study staff may perform consent in-person at the time of recruitment if feasible and desired by the patient. The study visit will occur at the Chronic Pain and Fatigue Research Center, University of Michigan at Domino Farms. At the initial visit, Day 0, the informed consent process conducted by trained study staff, if not already completed. This will be followed by questionnaire completion using Qualtrics electronic data capture system, and orientation and training on the acupressure device and ambulatory mobile support technology. Table 1 indicates the timeline of the study and when questionnaires will be administered throughout the study. Day 1 treatment will occur via Zoom with the participant and a study coordinator. The participant will perform the treatment with the coordinator observing the technique and available to answer any questions the participant may have.

Participants will be provided with a pre-addressed, pre-paid box to return the AcuWand or may return it in person to the study team at Domino's Farms.

Table 1: Timeline of Study

	Day 0	Day 1	Day 7	Day 21	Day 42	Day 63
Initial visit						
Screening (if not done)	X					
Consent (if not done)	X					
Treatment		X-Zoom	X	X	X	
Questionnaires:						
Past Med/Surg Hx	X					
PROMIS 29+2	X			X	X	X
FMS	X			X	X	X
HAQ	X			X	X	X
RA disease activity	X			X	X	X
Desire for relief	X					
Expected relief	X					
Credibility					X	
Tolerability				X	X	
Acupr. sensation				X	X	
PGIC					X	
Phone call			X			

FMS = Fibromyalgia Survey Questionnaire. HAQ = Health Assessment Questionnaire. Acupr. Sensation = Acupressure sensation.

PGIC = Patient Global Impression of Change.

Clinical data. Participants will undergo an assessment of past medical history and pregnancy status. Medications (*especially analgesics including opioids*), diagnoses, pain interventions, and any relevant labs already collected for clinical purposes will be confirmed via EMR review.

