Questionnaires. All participants will complete a battery of validated questionnaires before, during and after completion of treatment intervention. Questionnaires will measure pain, sleep disturbance, fatigue, and depression given the increased rates of these outcomes in patients with RA. Questionnaires will also focus on acupressure expectations, tolerability, and acceptability. Questionnaires will be applied pre-treatment, at 3 and 6 weeks into treatment, and 3 weeks post-treatment intervention (see Table 1). Surveys will be sent via email, and if needed, reminder phone calls will also be utilized.

1.4.3 Study Procedures:

1.4.3a Acupressure Intervention Procedures

The self-acupressure intervention will be delivered using the modified MeTime Acupressure mobile app in addition to in-person or virtual instruction via study staff. The MeTime Acupressure app was developed in association with patient focus groups (six focus groups each of eight to ten women) and the University of Michigan 3D Media Laboratory (screen shot examples in Figure 2). The MeTime Acupressure app will be loaded onto computer tablets or smart phones by the participants.

Participants will also receive an AcuWand to be used in association with the acupressure app to help participants apply the correct amount of pressure to acupoints (See Figure 1).

Figure 1 AcuWand Device

relaxing acupoints are:

[figure not shown]
- *Point 1: Yin tang (Unilaterally)*
- *Point 2: Anmian (EX17) (Bilaterally)*
- *Point 3: Heart 7 (HT7) (Bilaterally)*
- *Point 4: Spleen 6 (SP6) (Bilaterally)*
- *Point 5: Liver 3 (LV3) (Bilaterally)*

Figure 2 Sample MeTime Acupressure App

There are 5 acupoints with 4 of the acupoints performed on both the left and right sides of the body (total of 9 points to stimulate; see Figure 3. The

Figure 3 Relaxing Acupressure

Participants will be introduced to the MeTime App and AcuWand device at their initial clinic visit. A research team member will provide the patient with instructions and guide the patient through using the app, the AcuWand and performing Self-Acupressure. Study participants will be told to perform acupressure once per day and to stimulate each point a circular motion for three minutes. There are 9 acupressure points, totaling 27 minutes of stimulation per day. Participants will perform daily acupressure for a total of six weeks.

1.4.3b Participant Adherence

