1.5 Statistical Design

Due to the pilot and feasibility nature of this study, we will primarily be using descriptive statistics. We will obtain pre-, during and post-treatment measures of disease activity and symptoms (pain, sleep disturbance, fatigue, and mood). These measures will be analyzed with t-test or appropriate non-parametric test if data not appropriate. This is an open study.

Aim 1: We will compare number of acupressure treatments performed to the number of total number of sessions required. We would consider successful feasibility to be over 80% of sessions completed.

Aim 2: We will compare scores for pain, fatigue, and sleep on pre-treatment and post-treatment surveys with paired t-test to assess for significance.

Aim 3: We will explore pre-treatment and post-treatment RA disease activity scores with paired t-test to assess for significance.

This is a pilot study and we do not expect that we will achieve statistical significance. With the sample size of 30 we would only be able to detect a difference between pre and post scores would be approximately 0.5 standard deviation.

References:

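### Does it matter that Aims 2 and 3 do not name the study day meant by post-treatment?

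*Combined protocol and SAP*

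**What the plan says.** Section 1.5 states Aim 2 as "We will compare scores for pain, fatigue, and sleep on pre-treatment and post-treatment surveys with paired t-test to assess for significance" and Aim 3 as "We will explore pre-treatment and post-treatment RA disease activity scores with paired t-test to assess for significance". Neither sentence gives a study day. The opening paragraph of the same section is wider. It says "We will obtain pre-, during and post-treatment measures of disease activity and symptoms" and submits those measures to a t-test or a non-parametric alternative, within an analysis described as mainly descriptive.

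The schedule is in section 1.4.2: "Questionnaires will be applied pre-treatment, at 3 and 6 weeks into treatment, and 3 weeks post-treatment intervention (see Table 1". Table 1 in that section places PROMIS 29+2, the Fibromyalgia Survey, the HAQ and RA disease activity on Days 0, 21, 42 and 63. Section 1.4.3a adds "Participants will perform daily acupressure for a total of six weeks", so Day 42 closes the treatment period and Day 63 is a follow-up visit.

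**The concern.** Two visits could serve as the second half of each pair, and they answer different questions. Day 42 shows the change reached by the end of six weeks of daily acupressure. Day 63 shows what remains three weeks after it stops. Two analysts could each follow section 1.5 faithfully and test different data for pain, which is the secondary outcome, and for fatigue, sleep and disease activity, which are exploratory.

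The result is also meant to be used later. Section 1.1 says "This study will allow us to better estimate the needed sample size and to focus on specific primary outcome measures for future studies". If the effect fades after treatment, or the spread of the changes differs between visits, the planning figures depend on the visit. Leaving the day open also leaves room to lead with whichever visit looks better.

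**Working it through.** **Step 1: map the labels to days.**

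| Day | Label in section 1.4.2 | Treatment marked in Table 1 | Aim 2 and 3 outcomes collected |
|---|---|---|---|
| 0 | before treatment | no | yes |
| 21 | 3 weeks into treatment | yes | yes |
| 42 | 6 weeks into treatment | yes | yes |
| 63 | 3 weeks after treatment | no | yes |

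The three phases named at the start of section 1.5 fit this table: Day 0 is before, Days 21 and 42 are during, and Day 63 is after. On these labels, the literal reading of Aims 2 and 3 is Day 0 against Day 63. Another sentence in section 1.4.2, "All participants will complete a battery of validated questionnaires before, during and after completion of treatment intervention", fits Day 63 at least as well as Day 42. Pointing the other way, the global impression of change and the credibility questionnaire are scheduled at Day 42 only. The documents lean to Day 63, but section 1.5 does not tie the aims to it.

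**Step 2: reproduce the plan's own figure.** Section 1.5 says that 30 participants can detect a pre-post difference of about 0.5 SD. It gives no alpha, sidedness or power, so I assume two-sided 5%, 80% power and 30 complete pairs.

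- Normal approximation: (1.960 + 0.842)/√30 = 2.802/5.477 = 0.51 SD of change.
- Exact noncentral t with 29 degrees of freedom: 0.53 SD.

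Both agree with the stated figure. With 30 complete pairs, the choice of visit does not alter it.

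**Step 3: the cost of choosing the visit after seeing the data.** Suppose there is no true change, both visits are tested at two-sided 5%, and either one counts.

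- Independent changes (upper reference): 1 − 0.95² = 9.75%.
- Correlated changes (simulation, 200,000 studies of 30 pairs): 9.1% at correlation 0.5, 8.5% at 0.7 and 7.1% at 0.9.

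The documents give no correlation, so these values are assumptions. Two measurements three weeks apart on the same person, each taken as change from the same baseline, would be expected to correlate well above zero. The inflation per outcome is therefore about 2 to 4 percentage points.

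**Step 4: larger figures that do not measure the missing label.**

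- *Same true change at both visits.* With 0.3 to 0.5 SD and correlation 0.5 to 0.9, the two tests disagree on significance in 12% to 34% of studies. This is sampling noise between two imperfectly correlated tests, and it would remain if the day were named.
- *Effect fading after treatment.* If a Day 42 change of 0.50 SD falls to 0.375 or 0.25 SD by Day 63, power with 30 pairs drops from 75% to 51% or 26%. A future two-arm trial at 80% power needs 2 × 2.802²/d² per arm, which is 63, 112 or 252 for d = 0.50, 0.375 or 0.25. The fading is assumed. If it happened, data from both visits would show it.
- *Different spread at the two visits.* With equal SDs, the variance of change is proportional to 1 − r, where r is the correlation with baseline. If r is 0.7 at Day 42 and 0.6 or 0.5 at Day 63, the ratio is 0.4/0.3 = 1.33 or 0.5/0.3 = 1.67. This also describes the data. A planner would take the SD from whichever visit the next trial adopts, and both are available.

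**The case for a change.** The best case for a change is that it costs almost nothing. Both aim sentences speak of assessing significance, pain is a named secondary outcome, and the pilot is meant to inform the next trial. The schedule wording is a collection timetable that section 1.5 never cites. Read literally, it leaves the aim sentences with no end-of-treatment comparison, which many readers would expect to be the main one. One phrase naming the day would end the doubt and remove any freedom to choose later.

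Part of this stands. The day is not written down, the labels do not settle it beyond argument, and naming it would be tidier. But the argument does not show that anything planned is wrong. Either day gives a valid paired comparison, and there is no statistical ground for preferring one: a correction would have to accept Day 42 or Day 63, whichever the sponsor intends. Nor is an end-of-treatment comparison excluded, because the opening paragraph of section 1.5 covers measures taken during treatment as well as after it.

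**Conclusion.** This is an unwritten definition, not a faulty rule, and the plan does not need to change. The primary outcome, feasibility and acceptability judged by sessions completed and the acceptability questionnaire, does not depend on the visit. For the other outcomes, the measured harm is a false-positive rate per outcome of about 7% to 9% instead of 5%. It arises only if the more favourable visit is selected, and it rests on two-sided 5% tests, 30 complete pairs and an assumed correlation of 0.5 to 0.9. In an uncontrolled pilot that disclaims any expectation of significance, no conclusion about efficacy turns on that difference. The larger figures for fading effects and sample size rest on assumed values and describe how two visits might differ. They are not a consequence of the missing label. A competent analyst would summarise change from baseline at Days 21, 42 and 63, label each by day, and let planners of the next trial use the visit that matches their design. The schedule already collects everything needed for that.
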